^a Some of the assessments referred to in this section may not be captured as data in the eCRF. They are intended to be used as safety monitoring by the treating physician. Additional testing or assessments may be performed as clinically necessary or where required by institutional or local regulations.

Table 2-5: Follow-up Assessments (All Participants)			
Procedure	Follow-Up^a Visits 1 and 2	Survival^b, Follow-up Visits	Notes
Safety Assessments			
Targeted Physical Examination	X		To assess for potential late emergent study drug related issues
Adverse Events Assessment	X	X*	*Beyond 100-114 days from the last dose of study therapy, participants will be followed for ongoing drug-related AEs until resolved, return to baseline or deemed irreversible, or until lost to follow-up or withdrawal of study consent.
Laboratory Tests	X		On site/local CBC w/differential, AST, ALT, ALP, T.Bili, BUN or serum urea level, creatinine and TSH for X01, repeat at X02 if study drug related toxicity persists.
Pregnancy Test (WOCBP Only)	X		Serum or urine
Review of Concomitant Medication	X		
[REDACTED]			
[REDACTED]	[REDACTED]	[REDACTED]	[REDACTED]
[REDACTED]	[REDACTED]		[REDACTED]
[REDACTED]	[REDACTED]		[REDACTED]
Survival Status			
Collection of Survival information	X	X	Every 3 months, until death, lost to follow-up, or withdrawal of study consent for 5 years following start of therapy. May be performed by phone contact or office visit, to include subsequent anti-cancer therapy

Table 2-5: Follow-up Assessments (All Participants)			
Procedure	Follow-Up^a Visits 1 and 2	Survival^b, Follow-up Visits	Notes
Efficacy Assessments			

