Tumor Assessments			
FIRST tumor assessment should be performed at Week 12 (± 1 week) following first dose. SUBSEQUENT tumor assessments should occur every 8 weeks (± 1 week) up to first 13 months, then every 12 weeks until disease progression or treatment discontinuation, whichever comes later.
 
CT/MRI of the chest, abdomen, pelvis and all known sites of disease. Use same imaging method as was used at screening/baseline.
 
CT with oral and intravenous contrast or contrast-enhanced MRI are the preferred imaging modalities. If CT iodinated contrast is contraindicated, a non-contrast CT of the chest, and contrast enhanced MRI abdomen, pelvis and all other known or suspected sites of disease should be imaged. (See Section 7.7.2.3).
 
Participants with a history of brain metastasis perform surveillance CT/MRI approximately every 12 weeks, or sooner if clinically indicated.
 
Tumor assessments will be performed at Weeks 12, 20, 28, 36 etc. (± 1 week) following first dose, up to first 13 months, and then every 12 weeks. These time points are independent of dosing.

^a Participants must be followed for at least 100 days after last dose of study treatment. Follow-up visit 1 (FU1) should occur 30 days from the last dose (+/- 7) days or can be performed on the date of discontinuation if that date is greater than 42 days from last dose. Follow-up visit #2 (FU2) occurs approximately 100 days (± 7 days) from last dose of study drug. Both Follow Up visits should be conducted in person.

^b Survival Follow-up visits to occur every 3 months (+/- 14 days) from Follow-up Visit 2. Survival visit may be conducted in person or by telephone. BMS may request that survival data be collected on all treated participants outside of the 3 month specified window. At the time of this request, each participant will be contacted to determine their survival status unless the participant has withdrawn consent for all contact.

Note: Some of the assessments referred to in this section may not be captured as data in the eCRF. They are intended to be used as safety monitoring by the treating physician. Additional testing or assessments may be performed as clinically necessary or where required by institutional or local regulations.

[REDACTED]

[REDACTED]

[REDACTED]

[REDACTED]

[REDACTED]

[REDACTED]

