9.2.3 Follow-up of AEs and SAEs

- Nonserious AEs should be followed to resolution or stabilization, or reported as SAEs if they become serious (see [Appendix 9](#)).
- Follow-up is also required for nonserious AEs that cause interruption or discontinuation of study treatment and for those present at the end of study treatment as appropriate.
- All identified nonserious AEs must be recorded and described on the nonserious AE page of the CRF (paper or electronic). Completion of supplemental CRFs may be requested for AEs and/or laboratory abnormalities that are reported/identified during the course of the study.

After the initial AE/SAE report, the investigator is required to proactively follow each participant at subsequent visits/contacts. All SAEs, and non-serious AEs of special interest (as defined in [Section 9.2](#) will be followed until resolution, until the condition stabilizes, until the event is otherwise explained, or until the participant is lost to follow-up (as defined in [Section 8.3](#)).

Further information on follow-up procedures is given in [Appendix 9](#).

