4 ENDPOINTS

4.1 Primary Endpoint

The primary endpoint is the incidence of high grade (Grade 3-4 and Grade 5) IMAEs.

IMAEs are specific events (or groups of PTs describing specific events) that include pneumonitis, diarrhea/colitis, hepatitis, nephritis/renal dysfunction, rash, endocrine (adrenal insufficiency, hypothyroidism/thyroiditis, hyperthyroidism, diabetes mellitus, and hypophysitis), and other specific events, considered as potential immune-mediated events by investigator that meet the definition summarized below:

1. Those occurring within 100 days of the last dose
2. Regardless of causality
3. With no clear alternate etiology based on investigator assessment, or with an immune-mediated component
4. Treated with immune-modulating medication (Of note, adrenal insufficiency, hypothyroidism/thyroiditis, hyperthyroidism, diabetes mellitus, and hypophysitis are considered IMAEs regardless of immune-modulating medication use, since endocrine drug reactions are often managed without immune-modulating medication).

The followings are the list of IMAEs in this study: skin, endocrinopathy, gastrointestinal, hepatic, renal, pulmonary, and neurologic adverse events.

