4.2 Secondary Endpoints

The secondary objective of the study will be assessed by measuring the following:

1. Characterization of outcome of all high grade (Grade 3-4 and Grade 5) IMAEs: Time to onset, time to resolution and percentage of subjects who received immune modulating medication will be analyzed for high grade (Grade 3-5) IMAEs of interest. Time to onset is calculated from first dosing date to the IMAE event onset date. Time to resolution is calculated from the IMAE onset date to IMAE end date. If an IMAE is ongoing at the time of analysis, the time to resolution will be censored at the last contact date. Management of high-grade (Grade 3-5) IMAEs will be characterized according to the following for all treated subjects:
 1. Percentage of participants who received immune modulating medication (or hormonal replacement therapy),
 2. Percentage of participants who received ≥ 40 mg prednisone equivalents,
 3. Total duration of all immune modulating medications given for the event.
2. PFS 1: PFS 1 is defined as the time from first dose to the date of the first documented PD as determined by the investigator (per RECIST 1.1 criteria or clinical) or death due to any cause whichever occur first. Subjects who die without a reported PD and without subsequent anti-cancer therapy will be considered to have progressed on the date of their death. Subjects who did not progress or die will be censored on the date of their last evaluable tumor assessment. Subjects who did not have any on-study tumor assessments and did not die will be censored on the date of first dose. Subjects who received any subsequent anti-cancer therapy without a prior reported progression will be censored at the

last evaluable tumor assessment prior to or on the date of initiation of the subsequent anti-cancer therapy.

Table 4.2-1: Censoring Scheme Used in Primary Analysis of PFS 1

Situation	Date of Progression or Censoring	Outcome
No baseline tumor assessments	First dose	Censored
No on study tumor assessments and no death	First dose	Censored
Progression documented between scheduled visits (per RECIST 1.1 criteria or clinical)	Date of the first documented tumor progression	Progressed
No progression, no death	Date of last tumor assessment with no documented progression	Censored
New anticancer treatment started without a prior reported progression	Date of last tumor assessment prior to or on the date of initiation of the subsequent anti-cancer therapy	Censored

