7.1 General Methods

In general, unless expressly stated otherwise, all analyses will be performed by separated Cohort 1, Cohort 2, Cohort 3 and Cohort 4. Except where otherwise stated in this SAP, all analyses and summaries will be performed for all treated subjects. Analyses based on the combination of Cohorts 2-4 are considered not necessary for CSR as Cohort 4 has low KPS and tolerability may not be the same with other groups.

Unless otherwise noted, the bulleted titles in the following subsections describe tabulations of discrete variables, by the frequency and proportion of subjects falling into each category, by cohorts (with total). Percentages given in these tables will be rounded and, therefore, may not always sum to 100%. Continuous variables will be summarized by cohort (with total) using the mean, standard deviation, median, minimum and maximum values.

Time to event distribution (i.e. progression free survival, overall survival and duration of response) will be estimated using Kaplan Meier (KM) techniques. When appropriate, the median along with 95% CI will be provided using Brookmeyer and Crowley methodology (using log-log transformation for constructing the confidence intervals). Rates at fixed timepoints (e.g. PFS 1 at 6 months) will be derived from the Kaplan Meier estimate and corresponding confidence interval will be derived based on Greenwood formula for variance derivation and on log-log transformation applied on the survivor function $S(t)$.

The CA209 Core Safety DPP refers to several analyses that are to be performed on subjects with extended follow-up. For these summaries, AEs occurring from the time of the first dose of study therapy through 100 days after the last dose of study therapy will be summarized. Further general methods information for the safety analyses, including general methods for AEs and laboratory tests can be found in Section 7.1 of the IO core SAP.

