7.6.2 Secondary Analyses

7.6.2.1 Characterization of Outcome of High Grade Immune-Mediated Adverse Events

Time to onset and time to resolution will be analyzed for high grade (Grade 3-5) IMAEs of interest. The IMAEs of interest are the followings: skin, endocrinopathy, gastrointestinal, hepatic, renal, pulmonary, and neurological adverse events. Median values using the Kaplan-Meier (KM) product limit method with 95%CI using Brookmeyer and Crowley method will be presented for all treated subjects.

Analysis of endpoints related to management of high-grade (Grade 3-5) IMAEs will be conducted based on General Methods specified in [Section 7.1](#).

[Redacted]

[Redacted]

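### Concomitant-medication review ends at Follow-up Visit 2, so the duration of immune-modulating treatment for late or long high-grade IMAEs is liable to be understated; the AE follow-up footnote also conflicts with Section 9.2.3

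*Protocol*

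**What the plan says.** **Collection.** In Protocol Table 2-5 the row "Review of Concomitant Medication" is marked for Follow-up Visits 1 and 2 and blank for the survival visits. On timing, the table note says "Follow-up visit #2 (FU2) occurs approximately 100 days (± 7 days) from last dose of study drug". Survival contacts follow every 3 months (± 14 days), in person or by telephone. AE assessment is marked at those contacts too, with a limiting footnote: "Beyond 100-114 days from the last dose of study therapy, participants will be followed for ongoing drug-related AEs until resolved", or until return to baseline or judged irreversible.

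**Definition.** An IMAE may start up to 100 days after the last dose and counts "Regardless of causality" (SAP 4.1; likewise Protocol 9.2.1.1, whose heading names IMAEs as the AEs of special interest). Protocol 9.2.3 says "All SAEs, and non-serious AEs of special interest" are followed to resolution, stabilization or another explanation, or until loss to follow-up. It sets no causality condition and no day-100 stop.

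**Analysis.** SAP 4.2 lists, within the first secondary endpoint, "Total duration of all immune modulating medications given for the event". SAP 7.6.2.1 says "Analysis of endpoints related to management of high-grade (Grade 3-5) IMAEs will be conducted based on General Methods", referring to SAP 7.1, which says "Continuous variables will be summarized by cohort (with total) using the mean, standard deviation, median, minimum and maximum values". For time to resolution the SAP does censor events that have not resolved: at last contact date in 4.2, and at the last date known alive in Appendix 3.

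**The concern.** A medication duration needs a start and a stop date. The schedule stops asking about medication at about day 100, while the events being treated may begin at about day 100. The courses most likely to be open at the last review are the late-starting and the long ones, so the loss is selective and pulls the summary down. The trial's stated purpose is to describe high-grade IMAEs and their outcome, and the length of immune-modulating treatment is part of that description.

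The second matter is a conflict between two instructions. Protocol Section 9 makes adherence to the Schedule of Activities mandatory. A site that follows the Table 2-5 footnote can stop assessing an ongoing non-serious IMAE that it rated unrelated to study drug. A site that follows 9.2.3 cannot.

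**Working it through.** The documents give no figure for this point, so there is none to reproduce. The check is day arithmetic, plus a comparison of the two follow-up rules.

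**Inputs.** FU2 day F = 100 ± 7, so 93 to 107 (Table 2-5). IMAE onset up to day 100 after last dose (SAP 4.1). Course length L is an assumption: the documents give no distribution, and the only taper length visible is a minimum of 1 month for pneumonitis (Protocol 8.1.2). I use 30, 56 and 84 days.

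**When a course outlasts the last review.** A course starting d days after last dose and lasting L days runs past FU2 if d + L > F. The earliest affected start is therefore d = F − L + 1.

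| Assumed L | F = 93 | F = 100 | F = 107 |
|---|---|---|---|
| 30 days | day 64 | day 71 | day 78 |
| 56 days | day 38 | day 45 | day 52 |
| 84 days | day 10 | day 17 | day 24 |

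**How much is lost.** If nothing is recorded after FU2, the recorded part is F − d. For an assumed 84-day course starting on day 70 (ending on day 154), this is 93 − 70 = 23 to 107 − 70 = 37 days. That is 23/84 = 27% to 37/84 = 44% of the course.

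**Which events this reaches.** An event that itself stops treatment will usually start before the next dose would have been due. Scheduled intervals in the protocol are 3, 4 or 6 weeks (21 to 42 days). With F = 100, such a course must last more than 100 − 42 = 58 days (onset on day 42) or 100 − 21 = 79 days (onset on day 21) to outlast FU2. For these events only long courses are affected. For events starting near day 100, almost any course is.

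**Analysis rule.** SAP 7.6.2.1 gives Kaplan-Meier methods for time to onset and time to resolution, and refers the management measures to 7.1. For continuous variables, 7.1 gives summary statistics only. No visible text says what to do with a course still open.

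**The two follow-up rules after FU2.**

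| Event ongoing after FU2 | Table 2-5 footnote | Section 9.2.3 |
|---|---|---|
| IMAE rated drug-related | followed | followed |
| Serious IMAE rated unrelated | not covered | followed (Appendix 9 agrees) |
| Non-serious IMAE rated unrelated | not covered | followed |

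The practical gap is the last row, because SAE follow-up is stated twice elsewhere. If the table is followed there, AE assessment ends at about FU2, but the event is censored at a later contact or last-known-alive date. Illustration: onset on day 70 and last AE assessment on day 100 give 30 days observed. If the next survival contact is about 90 days later (day 190), the event is carried as unresolved for 190 − 70 = 120 days, even if it resolved in between. This tends to lengthen the estimated time to resolution.

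**The case against.** The strongest reply on medication is that a blank cell in one table does not prove absence of collection. Appendix 9 calls for additional case-report-form information on potentially immune-mediated events, Section 9.2.3 allows supplemental forms, and SAE reports must be updated. Part of Protocol Section 7 is blacked out. The SAP also defers conventions to a core SAP and table details to a data presentation plan, neither of which is available here. This stands as a limit on certainty: some stop dates may be captured by another route. It does not close the gap, because neither the content nor the time limit of the additional information is stated, and the schedule is the document that sites are told to follow.

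It is also fair that the measure is one descriptive item with no test attached, and that the 40 mg prednisone-equivalent item is yes/no, so a missing stop date does not change it.

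Three stronger readings are tempting, and the documents do not support them:

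- *IMAE resolution is cut off at about day 100.* The footnote itself extends follow-up of drug-related AEs past FU2, Section 9.2.3 covers every IMAE, and events still unresolved are censored.
- *Events drop out of the primary numerator because their treatment was never recorded.* This would need a non-endocrine high-grade event with onset by day 100, first treated after FU2, whose treatment is missing from the AE record as well. Nothing says that the treatment criterion is judged only from the scheduled medication review.
- *Truncated courses will be analysed as complete.* No text says so. The supportable statement is that no visible rule covers them, so they may be truncated or left out.

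**Conclusion.** The point holds for medication duration. As scheduled, collection ends on day 93 to 107, and a course open at that time has neither a planned stop date nor a stated analysis rule. Whether such courses are truncated or omitted, the longest lose most, so the bias is downward. In the worked example 27% to 44% of the course is recorded, but that rests on an assumed start, an assumed length and no other source of data. The number of courses affected cannot be derived from the documents.

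The footnote conflict is real but narrow. It bites on non-serious IMAEs rated unrelated and still ongoing after FU2, at sites that follow the table. Its effect runs the other way, towards a longer time to resolution. The primary endpoint is not shown to be affected. The changes are worth making because they are specific and cheap, and they remove a predictable bias from a secondary measure.

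**What to change.** 1. **Table 2-5, medication row.** For participants with an IMAE unresolved at FU2, record immune-modulating medication and hormone replacement at the existing 3-monthly survival contacts, until the medication is stopped or the event is closed.
2. **Table 2-5, AE footnote.** Extend the follow-up after day 100-114 to ongoing drug-related AEs and all IMAEs regardless of causality, to match Section 9.2.3.
3. **SAP 7.6.2.1.** Analyse medication duration by Kaplan-Meier, with courses ongoing at the last medication collection censored at that date.

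The cost is one table row, one footnote, one SAP sentence and a few extra form entries for a minority of participants, at contacts that already take place. The SAP change needs no new data and is worth making even if collection stays as it is.

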9.2.1.1 Adverse Events of Special Interest – Immune-mediated AEs

Immune-mediated AEs (IMAEs) are specific events (or groups of PTs describing specific events) that include pneumonitis, diarrhea/colitis, hepatitis, nephritis/renal dysfunction, rash, endocrine (adrenal insufficiency, hypothyroidism/thyroiditis, hyperthyroidism, diabetes mellitus, and hypophysitis), and other specific events, considered as potential immune-mediated events by investigator, that meet the definition summarized below:

- those occurring within 100 days of the last dose
- regardless of causality
- with no clear alternate etiology based on investigator assessment, or with an immune-mediated component
- treated with immune-modulating medication (Of note, adrenal insufficiency, hypothyroidism/thyroiditis, hyperthyroidism, diabetes mellitus, and hypophysitis are considered IMAEs regardless of immune-modulating medication use, since endocrine drug reactions are often managed without immune-modulating medication).

[Table 9.2.1.1-1](#) below provides a summary of the IMAEs category and their respective preferred terms.

Table 9.2.1.1-1: Preferred Terms Included in Analysis of IMAEs to Support Warnings and Precautions

IMAE Category	PTs included under IMAE Category
Pneumonitis	Pneumonitis, interstitial lung disease
Diarrhea/Colitis	Diarrhea, colitis, enterocolitis
Hepatitis	Hepatotoxicity, hepatitis, hepatitis acute, autoimmune hepatitis, AST increased, ALT increased, bilirubin increased, ALP increased
Adrenal insufficiency	Adrenal insufficiency
Hypothyroidism/Thyroiditis	Hypothyroidism, thyroiditis Thyroiditis acute (collapsed with thyroiditis for frequency), Autoimmune thyroiditis (collapsed with thyroiditis for frequency)
Hyperthyroidism	Hyperthyroidism
Hypophysitis	Hypophysitis
Diabetes mellitus	Diabetes mellitus, diabetic ketoacidosis
Nephritis and renal dysfunction	Nephritis, nephritis allergic, tubulointerstitial nephritis, acute renal failure, renal failure, increased creatinine
Rash	Rash, rash maculopapular

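### High-grade IMAEs count to 100 days after the last dose, but follow-up laboratory tests are unconditional only at FU1, so clinically silent late events may be under-ascertained

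*Protocol*

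**What the plan says.** **Endpoint window.** Protocol 9.2.1.1 limits IMAEs to "those occurring within 100 days of the last dose", and SAP 4.1 repeats the limit for the primary endpoint. Causality does not matter. Non-endocrine events must also have been treated with immune-modulating medication. Adrenal insufficiency, thyroid disorders, diabetes mellitus and hypophysitis count without it.

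**Terms found by blood test.** Table 9.2.1.1-1 places "AST increased, ALT increased, bilirubin increased, ALP increased" under hepatitis, increased creatinine under renal dysfunction, and has separate categories for diabetes mellitus and adrenal insufficiency.

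**Follow-up laboratory tests.** Table 2-5 lists "On site/local CBC w/differential, AST, ALT, ALP, T.Bili, BUN or serum urea level, creatinine and TSH for X01" (X01 is FU1). From its last two tests on, the entry reads "creatinine and TSH for X01, repeat at X02 if study drug related toxicity persists", so a repeat at FU2 (X02) depends on persisting drug-related toxicity. Glucose, sodium and potassium are on the on-study panels (Tables 2-2 to 2-4) but not on this one.

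**Visit timing.** Footnote a to Table 2-5 sets FU1 at 30 ± 7 days, or on the discontinuation date if that is more than 42 days after the last dose. It continues: "Follow-up visit #2 (FU2) occurs approximately 100 days (± 7 days) from last dose of study drug". The same footnote says: "Participants must be followed for at least 100 days after last dose of study treatment". The adverse event row of the same table narrows follow-up to ongoing drug-related events from a different boundary: "Beyond 100-114 days from the last dose of study therapy".

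**The concern.** The primary result is an incidence over a defined window, so the means of detection should cover that window. Here the laboratory part does not. A participant with no toxicity at FU1 has no required blood test for the rest of the 100 days. The trigger for a repeat is toxicity that is already known and judged drug-related, whereas the endpoint is about new events whatever their cause.

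Open-ended questioning about adverse events (Protocol 9.2.2) will not reveal a change that only a blood test shows. Whether such an event enters the numerator then depends partly on whether the participant was still on the treatment-phase testing schedule when it arose.

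In a safety trial a shortfall in detection errs in the reassuring direction. It matters more because SAP 7.1 reports the four cohorts separately, and two of them are planned at about 25 participants each.

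**Working it through.** **1. The plan's own precision figure (Protocol 10.1, SAP 5).** Half-width = 1.96 × √(p(1−p)/n).

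- n = 100: p = 0.34 gives 9.28%; p = 0.50 gives 9.80%. Stated: 9.3% to 9.8%.
- n = 200: p = 0.34 gives 6.57%; p = 0.50 gives 6.93%. Stated: 6.6% to 6.9%.

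The stated figures reproduce and are not in dispute. They describe sampling error only and serve below as a yardstick.

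**2. Days after FU1 without an unconditional laboratory test.** Gap = 100 − day of FU1.

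| FU1 on day | Gap (days) |
|---|---|
| 23 (30 − 7) | 77 |
| 30 | 70 |
| 37 (30 + 7) | 63 |
| 43 or later (late discontinuation) | 57 at most |

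**3. Position of FU2.** The earliest day is 100 − 7 = 93 and the latest is 100 + 7 = 107. An FU2 on day 93 leaves 100 − 93 = 7 days of the window after the last scheduled in-person review. An FU2 on or after day 100 leaves none. The range 93 to 107 does not match the 100 to 114 days in the adverse event row.

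**4. Which IMAE categories are exposed.**

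| Category | Relevant test on follow-up panel | Immune-modulating treatment needed to count |
|---|---|---|
| Diabetes mellitus | Glucose: absent | No |
| Adrenal insufficiency | Sodium, potassium: absent | No |
| Thyroid disorders | TSH: FU1, conditional at FU2 | No |
| Hepatitis | AST, ALT, ALP, bilirubin: FU1, conditional at FU2 | Yes |
| Nephritis and renal dysfunction | Creatinine: FU1, conditional at FU2 | Yes |

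For the endocrine rows, an undetected event is a direct loss from the numerator. For hepatic and renal events the loss is indirect: the event would have counted only if it had been detected and then treated with immune-modulating medication.

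**5. Scale, by assumption only.** The documents give no rate for late events detectable only by laboratory test. Let q be the share of treated participants whose only high-grade IMAE is such an event and goes undetected. The reported incidence is then low by q.

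- q = 1%, 2% or 5% understates incidence by 1, 2 or 5 points. Against the n = 100 half-width of 9.28 to 9.80 points, that is about 0.1, 0.2 or 0.5 of a half-width.
- One such participant moves the incidence by 1/100 = 1 point in Cohort 1, 1/50 = 2 points in Cohort 2, and 1/25 = 4 points in Cohort 3 or 4.

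**The case against.** The strongest reply is that other routes of detection exist. FU2 is in person, with adverse event assessment, a targeted examination aimed at late-emerging problems, and a medication review. Extra tests are allowed when clinically necessary. Clinically significant laboratory results must be recorded (Protocol 9.2.6), and potential drug-induced liver injury must be reported as serious (9.2.7). This stands for events that produce symptoms or prompt a test. It does not give uniform ascertainment of silent ones, because discretionary testing needs a prompt.

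A second reply also largely stands: an untreated rise in transaminases or creatinine is not an IMAE as defined, so failing to test for it does not by itself remove an endpoint event. That narrows the direct exposure to endocrine events. Hepatic and renal events remain exposed in so far as detection would have led to treatment.

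A reader might infer that ascertainment stops on day 93. The documents do not support that. Protocol 9.2.1 and Appendix 9 collect serious events within 100 days and non-serious events for at least 100 days, 9.2.3 follows events of special interest to resolution or stabilization, and survival visits also carry an adverse event assessment. Nor is the minimum of 100 days strictly contradicted by FU2 at 100 ± 7, since follow-up continues every 3 months afterwards. What remains is that the last scheduled medication review, which bears on whether a non-endocrine event qualifies, may precede day 100. The next survival contact comes about 3 months after FU2, and by then adverse event follow-up is limited to ongoing drug-related events.

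**Conclusion.** The mismatch between the endpoint window and the laboratory schedule is real. For participants without persisting drug-related toxicity at FU2, 63 to 77 of the 100 post-dose days have no required blood test, or at most 57 with a late FU1. Glucose, sodium and potassium are not required at either follow-up visit. Up to 7 days may follow the last scheduled safety visit.

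The supportable conclusion is that new, clinically silent high-grade events after FU1 may be under-ascertained. Any bias is downward. Its size cannot be derived, and the figures for q above are assumptions.

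Two stronger readings are not supported. One is that late events are in fact missed and the incidence is in fact biased: no document gives a rate for such events. The other is that Cohort 4 is affected more because low-KPS participants stop early. SAP 7.1 says only that tolerability in that cohort may differ. No figure for early stopping is given, and everyone who stops has the same follow-up schedule.

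The sample size and precision statements are unaffected.

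**What to change.** In Protocol Table 2-5:

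1. Draw the follow-up panel at both FU1 and FU2 in all participants, and add glucose, sodium and potassium, so that ascertainment of the primary endpoint matches its window.
2. Reconcile the three timing statements (100 ± 7 days, at least 100 days, 100 to 114 days) so that the closing adverse event and medication review falls on or after day 100.

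The SAP should then say how an abnormality first seen in an FU2 sample taken after day 100 is dated. Otherwise it could be found and still fall outside the count.

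If follow-up is already complete, state beside the primary result that laboratory ascertainment after FU1 was conditional and that the incidence may be understated for this reason.

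The cost is one extra local blood draw at an in-person visit that already takes place, three added analytes and a revised visit window. The reported incidence may come out slightly higher.
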